### **8.1.8 Planned Sensitivity and Subgroup Analyses**

Analysis of OS will be performed in the per protocol set. The same methodology as for analyses specified in Section 8.1.4 will be applied.

For randomized subjects, analysis for OS will be performed in the following subgroups:

- Prior history of brain metastases (yes versus no)
  - PCI (yes vs no) in subjects with no prior history of brain metastases
- Sensitivity to first line platinum-based regimen (sensitive [OR/SD after first line therapy and progression/recurrence-free interval  $\geq$  90 days] versus refractory/resistant [PD as best response to or  $<$  90 days progression/recurrence-free interval after first line therapy])
- LDH ( $>$  ULN vs.  $\leq$  ULN) at Screening
- Overall VALG stage (Limited Disease vs Extensive Disease) at initial diagnosis
- Gender
- Race

Difference in OS between rovalpituzumab tesirine and topotecan arms will be assessed by an unstratified log-rank test for each subgroup. Hazard ratios will be calculated by a Cox's model.

## **8.2 Safety Analyses**

Safety endpoints will be summarized using data from the Safety set. Safety analyses will involve examination of the incidence, severity, and type of treatment-emergent adverse events (TEAEs) reported, changes in vital signs and laboratory test results from baseline (the assessment prior to first dose) to specified time points throughout the study, and concomitant medications used. NCI CTCAE version 4.0 will be used in the grading of adverse events and laboratory abnormalities that are reported as adverse events.

### **8.2.1 Treatment-Emergent Adverse Events (TEAEs)**

TEAEs reported during the study will be coded using a MedDRA dictionary. Incidence of TEAEs will be summarized by treatment arm and the following:

- System organ class and preferred term
- System organ class, preferred term, and severity

These summaries will be presented for the following subsets:

- Serious TEAEs
- All TEAEs
- Drug-related TEAEs

For tables reporting AEs by severity, if a subject has multiple occurrences of an AE with the same organ class and preferred term, the most severe event will be presented.

### **8.2.2 Clinical Laboratory Evaluation**

Laboratory parameters will be summarized by treatment arm at each visit. Each summary will include the values of the laboratory parameters and changes from baseline. Shift

tables from baseline will be presented for laboratory values in the chemistry and hematology panels. Parameters will be classified according to the laboratory reference normal ranges. A listing will be provided for out-of-normal range as well as clinically significant abnormal lab values.

### **8.2.3 Vital Signs**

Vital signs including pulse, blood pressure, temperature, height, and body weight will be summarized by treatment arm and time point. For each assessment of vital signs, change from baseline will be summarized by treatment arm.

### **8.2.4 ECOG Performance Status**

ECOG performance status will be summarized for each visit by treatment arm. Shifts from baseline to the best and worst post-baseline score may be tabulated.

### **8.2.5 Electrocardiogram**

ECG status will be summarized for each scheduled visit by treatment arm. Shifts from baseline may be tabulated.

### **8.2.6 Concomitant Medications**

Concomitant medications will be classified according to the anatomical therapeutic chemical (ATC) codes in the World Health Organization Drug (WHODRUG) dictionary. The incidence rate of each coded concomitant medication will be tabulated by treatment arm. The table will be sorted by the incidence use of the entire sample.

## **8.3 Type I Error Adjustment Procedure for Multiple Testing**

To meet global regulatory requirements, a multiple testing strategy will be implemented to control the family-wise type I error ( $\alpha$ ) for comparisons of rovalpituzumab tesirine arm versus topotecan arm with respect to the primary and secondary endpoints in the order specified below.

The following null hypotheses are considered:

H1: Rovalpituzumab tesirine arm is not superior to topotecan arm in OS.

H2: Rovalpituzumab tesirine arm is not superior to topotecan arm in PFS.

H3: Rovalpituzumab tesirine arm is not superior to topotecan arm in PRO physical functioning scale at C2D1 for rovalpituzumab tesirine arm and C3D1 for topotecan arm.

H4: Rovalpituzumab tesirine arm is not superior to topotecan arm in ORR.

[figure not shown]
H5: Rovalpituzumab tesirine arm is not superior to topotecan arm in CBR.

H6: Rovalpituzumab tesirine arm is not superior to topotecan arm in DOR.

The family of null hypotheses will be tested using a hierarchical procedure, ie, in a fixed sequence of {H1, H2, H3, H4, H5, H6}. Hypothesis H1 will be tested first, and no further tests will be performed if H1 is not rejected. Thereafter, each hypothesis will be tested in the order specified if and only if H1 and all preceding null hypotheses are rejected.

Otherwise testing in the hierarchical sequence will stop. All the testing at final analysis will be carried out at one-sided 0.025 level of significance.

See flowchart below for illustration.

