Secondary time-to-event endpoints of PFS and DOR will be analyzed using the same statistical method described for the analysis of OS. Analysis of categorical endpoints such as ORR and CBR will be performed for the randomized subjects with measureable disease at baseline. Comparison of the categorical endpoints will be carried out using a one-sided Cochran-Mantel-Haenszel (CMH) test, stratified by the randomization stratification factors.

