## 8.0 Statistical Methods and Determination of Sample Size

Following the fourth safety review by the IDMC, on 04 December 2018 the IDMC recommended that enrollment in the study is discontinued due to overall survival concerns associated with the study drug. For patients currently on treatment in Arm A, the IDMC

recommends that sites and patients make individual decisions as to whether or not to continue treatment based on patient level response. The data collection plan has been minimized given the status change of this study. With all these changes, no statistical testing will be performed for the efficacy endpoints. The efficacy endpoints will be analyzed using the original statistical methodologies as appropriate. The efficacy endpoints for which there is not enough data to implement the statistical models will be summarized by treatment arms. The statistical section remains unchanged to reflect the original analysis plan.

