Objective response rate includes confirmed complete response (CR) and confirmed partial response (PR) assessed by the CRAC based on RECIST v1.1 from the date of randomization until disease progression or death, whichever comes first. A subject who did not meet CR or PR, including those who did not have post-baseline radiological assessments will be considered as non-responder.

Comparison of ORR will be carried out using a one-sided Cochran-Mantel-Haenszel (CMH) test, stratified by the randomization stratification factors. Odds ratio will be presented with two-sided 95% CI. The difference in ORR will be provided with two-sided 95% CI. Rates and corresponding 95% exact CI will be calculated by Clopper-Pearson method for each arm. Sensitivity analysis based on investigator-determined ORR will also be performed.

Clinical benefit includes complete response (CR), partial response (PR), and stable disease (SD) assessed by the CRAC based on RECIST v1.1 from the date of randomization until disease progression or death, whichever comes first. A subject who did not meet CR, PR, or SD, including those who did not have post-baseline radiological assessments, will be considered as non-responder. The same statistical methodology will be used as that for ORR endpoint.

A sensitivity analysis of ORR and CBR will be performed, accounting for subjects who initiated a new anti-cancer therapy. Modified endpoints of ORR and CBR, defined as rates of response from the date of randomization until initiation of new anti-cancer therapy/procedure, disease progression, or death, whichever comes first, will be analyzed using the same methodology as that for the endpoints of ORR and CBR.

Only subjects with an objective response will be included in the analysis of duration of response (DOR). DOR is defined as the time between the date of first response (CR or PR by CRAC, whichever is recorded first) to the date of the first documented tumor progression (assessed by CRAC per RECIST 1.1) or death due to any cause, whichever comes first. If a subject is still responding (i.e., has not progressed nor died after CR or PR), then the subject's data will be censored at date of the last radiographic assessment by CRAC. Methods for DOR analysis are similar to those described for the OS endpoint.

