5.1.3 Exploratory Objectives

The exploratory objectives are

- to determine if treatment with rovalpituzumab tesirine improves objective response rate (ORR);
- to compare the duration of objective response between two arms;
- to compare the safety and tolerability of rovalpituzumab tesirine to topotecan;

in subjects with advanced or metastatic DLL3^{high} SCLC who have first disease progression during or following front-line platinum based chemotherapy

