Distribution of the duration of response will be estimated for each treatment arm using Kaplan-Meier methodology. Median duration of overall response with corresponding 95% CI for each treatment arm will be provided. Due to the non-randomization nature of the analysis set for DOR, the analysis of DOR will be considered descriptive and will not be compared between treatment arms.

Patients Reported Outcomes (PRO)

The endpoints based on subject self-reported health related quality of life (QoL) and symptom assessments will be analyzed for post-treatment Week 3, Week 7 and subsequently with the increment of 6 weeks (i.e., Week 13, Week 19, and Week 24). The EORTC QLQ-C15-PAL/LC13 and the European Quality of Life-5 Dimensions (EQ-5D-5L) are used to measure the QoL and symptom assessments.

QLQ-C15-PAL & QLQ-LC13

The QLQ-C15-PAL is an abbreviated 15-item version of the EORTC QLQ-C30 for palliative care. The QLQ-C15-PAL questionnaire has four abbreviated scales measuring physical functioning, emotional functioning, nausea and vomiting, and fatigue. These

scales are estimated using the algorithm specified in *Addendum to the EORTC QLQ-C30 Scoring Manual: Scoring of the EORTC QLQ-C15-PAL* (July, 2006).

For each scale in QLQ-C15-PAL questionnaire, the raw score (RS) is computed as the mean of component items over the number of items answered for that scale if at least 50% of the items are answered, and set as missing otherwise. Then the scale score (SS) will be computed as:

$$SS = \{(RS - 1)/range\} \cdot 100.$$

The lung cancer module (QLQ-LC13) is composed of one multi-item scale to assess dyspnea, and a series of single items assessing coughing, sore mouth, dysphagia, peripheral neuropathy, alopecia, hemoptysis, and pain.

All scales and single items are reported on categorical responses, and will be linearly converted to 0 through 100 numeric values. Given a scale, the raw score (RS) is computed as the mean of component items over the number of items answered for that scale if at least 50% of the items are answered. It will be set as missing otherwise. Then the scale score, $SS = \{(RS - 1)/range\} \cdot 100$, will be computed.

For single-item measures (dyspnea, insomnia, appetite loss, constipation, diarrhea, and financial difficulties), none of the single-item measures can be computed if not answered. If a scale score cannot be computed, the outcome for that score is left blank.

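### The protocol still allows a responder-only hazard ratio for duration of response that SAP 11.2 rules out; the DOR text and objectives need to be aligned

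*Protocol*

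**What the plan says.** **Protocol.** DOR is a secondary endpoint (8.1.5), and the objectives in the synopsis and Section 4.0 are to compare it between arms. Only responders enter the analysis. Section 8.1.5 adds: "Methods for DOR analysis are similar to those described for the OS endpoint". The synopsis says the same: "Secondary time-to-event endpoints of PFS and DOR will be analyzed using the same statistical method described for the analysis of OS". Under Section 8.1.4 the OS methods are a stratified one-sided log-rank test, an Arm A over Arm B hazard ratio from a stratified Cox model, and Kaplan-Meier curves. Section 8.3 places DOR last in a fixed sequence of six superiority hypotheses: "H6: Rovalpituzumab tesirine arm is not superior to topotecan arm in DOR". It also states: "All the testing at final analysis will be carried out at one-sided 0.025 level of significance".

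**Amendment 4 text (Protocol 8.0 and synopsis).** After the IDMC recommendation to stop enrolment, no efficacy endpoint will be tested. The same paragraph continues: "The efficacy endpoints will be analyzed using the original statistical methodologies as appropriate". Endpoints with too few data to fit the models are to be summarized by arm, and the statistical section is left in place to show the plan as first written.

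**SAP.** DOR is exploratory and lies outside the four-step hierarchy of SAP 5.7.3. SAP 11.2 provides Kaplan-Meier estimates and medians with 95% CIs for each arm. Because the analysis set is not a randomized one, it says that "the analysis of DOR will be considered descriptive and will not be compared between treatment arms". Yet SAP 5.1.3 lists as an exploratory objective "to compare the duration of objective response between two arms", and SAP 11.1 puts exploratory comparisons at a nominal one-sided 2.5% level.

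**The concern.** Response is observed after randomization and treatment can affect it. Restricting the comparison to responders therefore gives up the protection of randomization. If one arm converts more patients into responders, and prognosis affects both response and duration, the two responder groups can differ in prognosis even when neither drug changes how long a response lasts. A hazard ratio between them then mixes any drug effect on duration with a difference in who responded.

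The SAP recognises this and drops the comparison; the protocol does not. Two programmers working from the same data, one from each document, could produce a between-arm DOR effect estimate or none. What is at stake is whether a secondary-endpoint hazard ratio is reported and read as a treatment effect. The OS result is not in question.

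**Working it through.** **1. Is a DOR hazard ratio still possible under the protocol?**

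| Question | Protocol | SAP |
|---|---|---|
| Status of DOR | Secondary, H6 of six | Exploratory, outside the hierarchy |
| Population | Responders only | Confirmed responders only |
| Between-arm test | Written in 8.3; cancelled by 8.0 | None (11.2) |
| Between-arm hazard ratio | OS methods kept where appropriate (8.0, 8.1.5) | None (11.2) |
| Objective | Compare arms (synopsis, 4.0) | Compare arms (5.1.3), against 11.2 |

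The Amendment 4 paragraph settles the test but not the hazard ratio. Its fallback to by-arm summaries depends on the amount of data, not on whether the analysis set is randomized.

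**2. The plan's own figures.** No sample-size or power figure is given for DOR. The OS calculation reproduces (Schoenfeld formula, HR 0.75, 2:1 allocation, one-sided 0.025, 85% power):

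- Deaths = (1.960 + 1.036)² / [(2/3)(1/3)(ln 0.75)²] = 489 after rounding up, as in Protocol 8.4.
- Critical HR = exp(−1.960/√(489 × 2/9)) = 0.829, and 6.5/0.8286 − 6.5 = 1.34 months, both as stated.

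DOR does not enter this calculation. H6 is last in the sequence, so setting it aside leaves alpha for H1 to H5 as it was.

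**3. How many responders?** Inputs: 444 enrolled (Protocol 8.4), taken as 296:148 at 2:1; topotecan response rate about 14% (Protocol 3.1); Rova-T 16% in third-line DLL3-high patients and 31% (8/26) in DLL3 ≥ 50% patients (Protocol 3.3).

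- Arm A: 296 × 0.16 = 47 to 296 × 0.31 = 92.
- Arm B: 148 × 0.14 = 21.
- Total: 68 to 112, over 3 × 2 × 2 = 12 strata, which is about 21/12 ≈ 1.7 topotecan responders per stratum.
- If every responder has an event, SE(log HR) = √(1/47.36 + 1/20.72) = 0.26 at the low end and √(1/91.76 + 1/20.72) = 0.24 at the high end. Power at HR 0.75 is then at most 19% to 22%.

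A Cox model can be fitted to 68 to 112 responders, so the protocol's data-volume clause does not clearly rule it out. The estimate would be imprecise.

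**4. How large could selection bias be?** This is an illustration with no treatment effect on duration. A latent standard-normal prognosis u raises both response propensity and duration, with duration = Exp(1) × exp(b·u). A subject responds if a latent propensity, correlated ρ with u, exceeds the cut-off that gives the arm's response rate. The values of b and ρ are assumptions. There is no censoring and no stratification.

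| Response rate, A v B | ρ = 0, b = 0.5 | ρ = 0.45, b = 0.5 | ρ = 0.71, b = 0.5 | ρ = 0.71, b = 0.3 to 0.8 (separate runs) |
|---|---|---|---|---|
| 14% v 14% | 1.01 | 1.00 | 1.01 | not run |
| 16% v 14% | 1.00 | 1.02 | 1.04 | 1.01 to 1.03 |
| 31% v 14% | 1.00 | 1.09 | 1.15 | 1.10 to 1.19 |

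Entries are Cox hazard ratios, A over B, among responders; differences of about 0.01 are simulation error. A larger repeat of the last column (2,000,000 per arm) gave 1.01 to 1.03 and 1.10 to 1.21. In this model the bias runs against the arm with more responders. It is absent when response is unrelated to prognosis or the response rates are equal.

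**The case against.** The strongest reply is that the documents, read together, already lead to the right place. Amendment 4 cancels every efficacy test and keeps Section 8.3 as a record. It applies the planned methods only where appropriate and provides by-arm summaries for thin data, which about 21 topotecan responders over 12 strata might well be. Protocol 8.1 leaves analysis detail to the SAP, and the SAP makes DOR descriptive. The SAP also calls itself a draft written against a draft amendment, and differs from the protocol elsewhere (497 deaths and an interim analysis, against 489 and none), so the DOR mismatch could be one symptom of that.

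Much of this stands. It shows that a DOR hazard ratio is not certain to be produced. It does not show that one is excluded: the fallback concerns data volume, the phrase about appropriateness is left to judgement, and SAP 5.1.3 contradicts SAP 11.2. Nor was Section 8.3 left wholly untouched, since Amendment 4 edited the wording of H6 and kept the hypothesis (Appendix L).

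A reader might infer more than the documents support:

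- **That H6 is a live confirmatory test with an inflated error rate.** Efficacy testing is cancelled. Even under the full sequence, H6 is reached only after H4, superiority in response rate for Arm A. With assumed rates of 10% versus 20%, an ungated log-rank test favoured Arm A in about 5% to 9% of simulations. But those rates are not in the documents, and H4 would be rejected for Arm A in only about 1.5 per million runs. At 31% versus 14%, where H4 could be passed, the simulated rejection rates for Arm A were 0.017, 0.009 and 0.007, all below 0.025.
- **That the hazard ratio is biased by a known amount.** The link between prognosis, response and duration is assumed. The 31% comes from 8 of 26 patients at a DLL3 cut-off of 50%, not this trial's 75%. Stratification could absorb some imbalance.
- **That the SAP forbids any comparison as a matter of principle.** It says only that none will be made.

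**Conclusion.** The inconsistency is real and worth correcting. The protocol still permits a between-arm DOR hazard ratio among responders, SAP 11.2 excludes it, and the SAP's own objective points the other way. Such a ratio is open to selection bias when response rates differ and response is related to prognosis.

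Under the illustrative model the spurious hazard ratio is negligible to small at 16% versus 14% and moderate at 31% versus 14%. At the expected numbers that shift would be hard to tell from sampling error: with a standard error of 0.24 to 0.26 on the log scale, a 95% interval around 1 runs from about exp(−1.96 × 0.26) = 0.60 to exp(1.96 × 0.26) = 1.66. Size and direction rest on assumptions that the documents do not give.

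The reach of the point is limited to how DOR is estimated and reported. The OS analysis, the sample size and the error control for H1 to H5 are unaffected.

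**What to change.** - **Protocol 8.1.5 and synopsis:** replace the sentences that apply the OS methods to DOR with the SAP 11.2 rule, namely Kaplan-Meier median with 95% CI by arm, and no between-arm test or hazard ratio.
- **Protocol 8.3 and synopsis:** mark H6 as not to be carried out. It need not be deleted if the section is to remain a record of the plan.
- **Objectives (synopsis, Protocol 4.0, SAP 5.1.3):** change the DOR objective from comparing the arms to describing DOR by arm. The general rule in SAP 11.1 for exploratory comparisons then has no DOR objective to attach to.

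The cost is wording. No sample size, event count or alpha changes, and the sponsor gives up only a between-arm DOR claim that its SAP already drops. If a between-arm measure of duration is wanted, mean DOR over all randomized subjects, with non-responders counted as zero and a fixed time horizon, would keep the randomized comparison. That is optional and not part of the correction.

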## 8.4 Determination of Sample Size

Following the fourth safety review by the IDMC, on 04 December 2018 the IDMC recommended that enrollment in the study is discontinued due to overall survival concerns associated with the study drug. 444 subjects were enrolled in the study. The following paragraph describes how the sample size was determined for the study.

The sample size of the study is primarily determined by the analysis of OS. Approximately 600 subjects in total will be randomized to rovalpituzumab tesirine

(Arm A) or topotecan (Arm B) in a 2:1 ratio. It is assumed that median overall survival in the topotecan arm (Arm B) will be around 6.5 months. Based on a log-rank test, at a one-sided significance level of 0.025 and a power of 85%, a total of 489 deaths are needed to detect an increase in median OS to 8.67 months in rovalpituzumab tesirine arm (Arm A), corresponding to a hazard ratio of 0.75 (i.e., a reduction in the hazard death of 25%). It is projected that an observed hazard ratio of 0.829 or less, corresponding to 1.34 months or greater improvement in median OS, would result in statistically significance in the final analysis of OS.

### **8.5 Interim Analysis**

No interim efficacy analysis is planned.

### **8.6 Accrual/Study Duration Considerations**

The total study duration and accrual duration are approximately projected to be 35 months and 24 months, respectively. A total of 600 subjects are expected to enroll during the accrual period.

### **8.7 Randomization Methods**

The randomization numbers of the study will assign to subjects in a 2:1 ratio to either receive 0.3 mg/kg rovalpituzumab tesirine or topotecan. Randomization will be stratified as follows:

- prior history of brain metastases (yes versus no),
- prior PCI (yes vs. no) for subjects with no prior history of brain metastases
- sensitivity to first line platinum-based regimen [sensitive (OR/SD after first line therapy and progression/recurrence-free interval  $\geq$  90 days) versus refractory/resistant (PD as best response to or  $<$  90 days progression/recurrence-free interval after first line therapy)],
- LDH level ( $>$  ULN vs.  $\leq$  ULN) at screening.

## **9.0 Ethics**

### **9.1 Independent Ethics Committee (IEC) or Institutional Review Board (IRB)**

Good Clinical Practice (GCP) requires that the clinical protocol, any protocol amendments, the Investigator's Brochure, the informed consent and all other forms of subject information related to the study (e.g., advertisements used to recruit subjects) and any other necessary documents be reviewed by an IEC/IRB. The IEC/IRB will review the ethical, scientific and medical appropriateness of the study before it is conducted. IEC/IRB approval of the protocol, informed consent and subject information and/or advertising, as relevant, will be obtained prior to the authorization of drug shipment to a study site.

Any amendments to the protocol will require IEC/IRB approval prior to implementation of any changes made to the study design. The investigator will be required to submit, maintain and archive study essential documents according to ICH GCP and all other applicable regulatory requirements.

Any serious adverse events that meet the reporting criteria, as dictated by local regulations, will be reported to both responsible Ethics Committees and Regulatory Agencies, as required by local regulations. During the conduct of the study, the investigator should promptly provide written reports (e.g., ICH Expedited Reports, and any additional reports required by local regulations) to the IEC/IRB of any changes that affect the conduct of the study and/or increase the risk to subjects. Written documentation of the submission to the IEC/IRB should also be provided to AbbVie.

